### 3.0 Protocol Synopsis

Study Summary					
Study Purpose	To determine the optimal bowel preparation regimen for Pure-Vu System procedures in patients indicate for colonoscopy procedure.				
Objective	The primary objective of this multicenter, prospective, randomized study is to evaluate the performance of Pure-Vu System in cleansing patients' colon who are indicated for a colonoscopy procedure using one of two different reduce bowel preparation regimes.in addition, the cecum intubation rate, time to cecum, total procedure time, and adverse event will be evaluated.				
Test and Comparator Procedures	Prep A	Prep B			
5 days prior procedure day					
No seedy food					
1 day prior procedure day					
Low residue diet;					
Spilt dose of 15 oz Magnesium Citrate + 39 oz of clear liquid		Spilt dose of 10 oz Magnesium Citrate + 32oz of clear liquid			
Procedure Day					
Clear-liquid diet up to 3 hours prior to the procedure					
Fasting (no food / liquids) start 3 hours prior to procedure time					
*At least 2 liter water per day during the preparation days.					

Document title:  Optimizing the Preparation Regime Prior to Colonoscopy Procedure with Pure-Vu System	Document No.  CL00042	Version  1.0	Page 8 of 61
---	------------------------------------	---------------------------	-----------------

Protocol Number	CL00042
Protocol Title	Optimizing the Preparation Regime Prior to Colonoscopy Procedure with Pure-Vu System Rev 1.0
Study Sponsor	Motus GI Medical Technologies, [name] [contact] [contact]
Sponsor Representative	[name] Director of Clinical Affairs
Study Type	Multicenter, prospective, randomized feasibility study
Study Product	Pure-Vu System
Study Phase	Post-market
IDE Number	K173392 Class II
Study Location	United States
Study Duration	Study period will last approx. 12 months
Study Design	Patients will be randomized to receive one of two bowel preparation regimens prior to colonoscopy with Pure-Vu procedure.
Planned Follow-Up	Telephone follow-up will be conducted at 2-3 working days post-procedure to assess subject well-being and capture any adverse events.
Subject Population	Subjects indicate for colonoscopy procedure

Document title:  Optimizing the Preparation Regime Prior to Colonoscopy Procedure with Pure-Vu System	Document No.  CL00042	Version  1.0	Page 9 of 61
---	------------------------------------	---------------------------	-----------------

Planned # of Subjects	Up to 100 subjects
Planned # of Sites	Up to 3 clinical sites
Primary Endpoint	The rate of adequate cleansing level per patient will be evaluated by the BBPS(1) scoring index post the cleansing operation in both study arms.
Secondary Outcomes	The following secondary outcomes will be determined : 
 
• Adverse events
 
• Cecal intubation rate
 
• Time to Cecum
 
• Total procedure time
 

Randomization	Block randomization will be employed for each site to assign subjects to one of the two bowel preparation arms (Prep A versus Prep B).
Eligibility Criteria	
Inclusion Criteria
 
 
1. Subjects scheduled for colonoscopy procedure
 
2. Subjects in the age range 22-75 years inclusive
 
3. Subject is willing and able to participate in the study procedures and to understand and sign the informed consent.
 
 
Exclusion Criteria
 
 
1. Patients with active Inflammatory Bowel Disease
 
2. Patients with known diverticulitis disease or with prior incomplete colonoscopy due to diverticular disease
 
3. Patients with known bowel obstruction
 
4. Patient with chronic constipation
 
5. History of prior surgery to colon and/or rectum
 

Document title:  Optimizing the Preparation Regime Prior to Colonoscopy Procedure with Pure-Vu System	Document No.  CL00042	Version  1.0	Page 10 of 61
---	------------------------------------	---------------------------	------------------

	

6. ASA <math>\geq</math> III

7. Renal insufficiency (Creatinine <math>\geq</math> 1.5mg /dL) (based on medical history)

8. Abnormal Liver enzymes (ALT/AST <math>\geq</math> 2 times upper limits of normal) (based on medical history)

9. Patients taking anticoagulants drugs (excluding aspirin) or dual antiplatelet therapy

10. Patients with known coagulation disorder (INR <math>></math>1.5).

11. Pregnancy (as stated by patient) or breast feeding

12. Patients with altered mental status/inability to provide informed consent

--	--

## Statistics

Primary Endpoint Analysis	
The primary endpoint is the rate of adequate bowel cleansing level, as determined by Boston Bowel Preparation Scale (BBPS), assessed per patient in both study arms.
 
Chi-square or Fisher's exact test, as appropriate, will be performed in order to compare the proportions of good or excellent cleansing level (i.e., BBPS>1 in all colon segments) post cleansing procedure between the two study arms.

Secondary Analyses	
Cecum intubation rate
 
Proportion tests (Chi-square or Fisher's exact) will be performed in order to compare between the two preparation procedures cecum intubation rate
 
Time analysis
 
T-tests for continuous variables will be performed in order to evaluated the difference between Prep A and Prep B for the following:
 

• Total procedure time

Document title:  Optimizing the Preparation Regime Prior to Colonoscopy Procedure with Pure-Vu System	Document No.  CL00042	Version  1.0	Page 11 of 61
---	------------------------------------	---------------------------	------------------

	

• Time to cecum

 
Safety analysis
 
Individual listings of adverse events including type of device, adverse events (reported term) start date, duration, and severity will be provided.

Determination of Sample Size	This is a pilot study that will include up to 100 patients; no statistical considerations were made to determine the sample size.
Interim analyses	No Interim analysis is planned.

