## 9.0 Study Design

This multicenter, prospective, randomized study will include up to 100 patients (30 patients per site and 15 patients per study arm), aimed at evaluating the performance of Pure-Vu System in cleansing patients' colon who are indicated for colonoscopy procedure using one of two different preparation regimes as detailed below.

[figure not shown]
Subjects will be enrolled at up to 10 clinical sites in the United States. Subjects who meet the eligibility criteria will be randomly allocated to a given study arm and will be required to follow a specific bowel preparation instruction along with a specific prep agent (Bowel preparation instructions for morning and afternoon procedures are provided in appendix B1 and B2, respectively), as per study arm allocation, starting 5 days prior to the colonoscopy with Pure-Vu. Patients will be asked to record and provide their diet and bowel movements in the provided diary log at time of their scheduled colonoscopy (Diary log is provided in appendix D).

In addition patient will be asked to complete a satisfaction questionnaire include feedback on the procedure and on specific aspects related to the preparation regime.

Following the procedure a telephone follow-up will be conducted at 48 hours ( $\pm$  48 hours) post Pure-Vu procedure to assess patient well-being and capture any adverse events.

Document title:	Document No.	Version	Page 22 of 61
Optimizing the Preparation Regime Prior to Colonoscopy Procedure with Pure-Vu System	CL00042	1.0	

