## 11.0 Study Procedures

### 11.1.1 Screening and Informed Consent (Visit 1)

Subjects participating in the study may be recruited from investigator's patients' pool.

A screening/baseline visit will be performed within 30 days prior to the scheduled Pure-Vu procedure to assess preoperative eligibility. In the event that the screening and eligibility assessment takes place more than 30 days prior to the planned procedure date, the investigator should contact the subject prior to the procedure date to assure there is no change in the subject's medical condition.

At the screening visit, subjects will be approached to obtain written informed consent prior to any study specific procedures being performed. The purpose of the study and the benefits and risks of the procedures will be explained to the subject and the consent process must be documented accordingly in the medical record. Subjects who agree to study participation must sign an IRB-approved ICF. Subjects will be informed that their participation in this study is voluntary and they may refuse to participate or discontinue from the study at any time. Subjects will be given the opportunity to ask the investigator questions so that they are adequately informed about the research. A copy of the signed informed consent must be provided to the subject and the informed consent process will be documented in source documents.

If new information becomes available that may affect a subject's decision to continue to take part in the study, this information will be discussed with the subject by the investigator.

Document title:	Document No.	Version	Page 26 of 61
Optimizing the Preparation Regime Prior to Colonoscopy Procedure with Pure-Vu System	CL00042	1.0	

The following assessments will be performed within 30 days prior to the scheduled procedure and the results recorded on the appropriate subject CRFs:

- Verification of eligibility criteria and subject risk per guidelines
- Demographics (age, gender, height, weight)
- Surgical and medical history (prior abdominal surgery, GI symptoms)
- General medical history will be assessed based on the subject's clinical condition

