## **12.0 Statistical Analysis**

### **12.1 Sample Size Determination**

This is a pilot study that will include up to 100 patients; no statistical considerations were made to determine the sample size.

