### **12.2 Description of statistical methods**

Basic demographic and other baseline characteristics will be collected and analyzed for all patients. Summary statistics (arithmetic mean, standard deviation, median, minimum and maximum for quantitative variables) will be presented for the total study population. Frequency tables for qualitative data will be provided.

Any deviation from specified statistical plan will be in addition to “per protocol” analysis and will be reported as such. Intent-To-Treat and Post-hoc analysis will be conducted according to the existing data gathered, if necessary.

In addition, in cases of an incomplete procedure (i.e., the entire colon is not visualized); the overall BBPS per patient will be evaluated based on the colon segments that were visualized.

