### Time analysis

T-tests for continuous variables will be performed in order to evaluate the difference between the two preparation procedures for the following endpoints:

- Time to Cecum- defined as the duration from colonoscope insertion to visualization of the cecum.

Document title:	Document No.	Version	Page 31 of 61
Optimizing the Preparation Regime Prior to Colonoscopy Procedure with Pure-Vu System	CL00042	1.0	

- Total Procedure time- defined as the time from colonoscope insertion to removal. (guide: >6 minutes withdrawal time)

These endpoints will be summarized using descriptive statistics, including number of subjects, mean, median, standard deviation, minimum, and maximum.

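### The time endpoints are compared by t-tests that use neither site nor the recorded baseline data; the tests are valid, but a prespecified adjusted model might give a modest gain in precision at little cost

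*Protocol*

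**What the plan says.** The synopsis (Statistics, Secondary Analyses) states: "T-tests for continuous variables will be performed in order to evaluated the difference between Prep A and Prep B for the following", and lists total procedure time and time to cecum. The body of the protocol (section 12.4, Time analysis) says the same: "T-tests for continuous variables will be performed in order to evaluate the difference between the two preparation procedures for the following endpoints". Neither place names a covariate or a site term.

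Section 11.1.1 lists "Demographics (age, gender, height, weight" among the screening items, under the lead-in "The following assessments will be performed within 30 days prior to the scheduled procedure and the results recorded on the appropriate subject CRFs". The physician's case report form (Appendix F) has fields for the same four items. The planned use of these data, in section 12.2, is descriptive: "Basic demographic and other baseline characteristics will be collected and analyzed for all patients", followed by summary statistics for the whole study population. That section also leaves room for post-hoc analyses if necessary, without naming any.

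Section 11.1.2 sets randomisation in blocks within each site. Section 9.0 gives the size as "up to 100 patients (30 patients per site and 15 patients per study arm" each, and section 12.1 says: "This is a pilot study that will include up to 100 patients; no statistical considerations were made to determine the sample size". The time endpoints are secondary (section 9.2), and section 12.7 acknowledges that the study is not powered.

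**The concern.** Time to cecum and total procedure time plausibly depend on the patient and the site as well as on the preparation. Age, sex, height and weight are known before the preparation is taken, so adjusting for them is legitimate. Site is built into the allocation. A plain two-sample t-test leaves whatever variation these factors explain in the error term. If they explain a useful share, the interval for the arm difference is wider than it need be. Site adds a second consideration: when allocation is balanced within site and sites differ in their usual times, an analysis that ignores site tends to overstate the standard error.

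At stake is the precision of two secondary comparisons. Section 12.7 says the study should show whether Prep B tends to do better, to inform later research, so tighter estimates serve its stated purpose. Prespecification matters because section 12.2 treats departures from the plan as additional analyses. An adjusted result produced afterwards would be open to the charge that its covariates were chosen with the data in view.

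**Working it through.** **There is no figure in the plan to reproduce.** The protocol states no SD, effect size, significance level or power for the time endpoints, and nothing on how well baseline data predict them.

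**Inputs from the protocol.** Up to 3 sites (synopsis) at 30 patients per site and 15 per arm per site (section 9.0) gives 3 × 30 = 90 patients, or 45 per arm. The stated maximum of 100 gives 50 per arm.

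**Assumed inputs.** Two-sided 5% level; SD 8 min; true difference 3 or 5 min; k = 3 patient covariates (age, sex, BMI); R2, the share of outcome variance that they explain, of 0, 0.05, 0.10 or 0.20.

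**Unadjusted t-test.** The standard error of the difference is 8 × √(2/45) = 1.687 min. The noncentrality is 3/1.687 = 1.78 or 5/1.687 = 2.96, on 90 − 2 = 88 degrees of freedom. Power from the noncentral t distribution is 42.1% or 83.5%.

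**Adjusted analysis.** Adjustment removes the explained variance but pays for estimating k coefficients. The expected ratio of the variance of the adjusted difference to the unadjusted one is (1 − R2) × (N − 3)/(N − k − 3). With N = 90 and k = 3 this is (1 − R2) × 87/84. Error degrees of freedom are 88 − 3 = 85.

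| R2 | Variance ratio | Worth in patients (1/ratio − 1) | Power, 3 min | Power, 5 min |
|---|---|---|---|---|
| Unadjusted | 1 | – | 42.1% | 83.5% |
| 0 | 1.036 | −3.4% | 40.8% | 82.1% |
| 0.05 | 0.984 | +1.6% | 42.6% | 84.0% |
| 0.10 | 0.932 | +7.3% | 44.5% | 85.9% |
| 0.20 | 0.829 | +20.7% | 48.9% | 89.6% |

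**Break-even.** The ratio equals 1 when R2 = 1 − 84/87 = 3.4%. At 50 per arm it is 1 − 94/97 = 3.1%. Below that, adjustment loses a little precision.

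**Check on the variance formula.** Simulation with four covariates at 50 per arm (8,000 runs per setting) gave variance ratios of 1.039, 0.991, 0.925 and 0.830 at R2 of 0, 0.05, 0.10 and 0.20. The formula with k = 4 gives 1.043, 0.991, 0.939 and 0.834.

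**Site.** The table covers the three patient covariates only. Three sites add two terms. Allocation is blocked within site, so these are close to balanced across arms and cost little beyond two further error degrees of freedom (85 − 2 = 83). The return depends on how much the sites differ, which the protocol does not say.

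**The case against.** The strongest reply is that nothing here is an error. A two-sample t-test of a randomised comparison is valid, and chance imbalance is already allowed for in its standard error and type I error. These are secondary endpoints of an acknowledged unpowered pilot, and a covariate set is often left to an analysis plan, which is not shown. All of that stands. What remains is that the protocol names the test twice and so makes a choice, and that choice leaves recorded data unused.

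Several stronger readings are tempting, but the document does not support them.

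- A reader might infer that precision is certainly being lost. No section says that age, sex or BMI predicts time to cecum or procedure time. The patient in section 6.3 whom the device could not pass beyond the sigmoid is a case of anatomy, which the proposed covariates would not capture.
- A reader might infer that R2 of 5–20% is worth 1/(1 − R2) − 1, or 5–25% more patients. That ignores the cost of estimating the coefficients; the table above gives 1.6–20.7%.
- A reader might infer that, because cleansing and cecal intubation were 99% and 98% in the earlier study, the time endpoints are the only place where the arms could separate. Section 12.4 also compares patient and user satisfaction between arms, and Appendix E asks about tolerability and disruption of the preparation. The earlier study also used a different, bisacodyl-based regimen.
- A reader might infer that adjustment is free. It spends degrees of freedom and does slight harm if the covariates are not prognostic.

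**Conclusion.** The point holds as a minor efficiency suggestion. The protocol fixes unadjusted t-tests for both time endpoints and uses neither the four recorded baseline items nor the site structure of its own randomisation. The comparison is unbiased as it stands; precision may be lost, by an amount that the document cannot settle.

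Under the stated assumptions the trade is lopsided but small. If the three patient covariates explain nothing, power falls by 42.1 − 40.8 = 1.3 points (3 min) or 83.5 − 82.1 = 1.4 points (5 min). If they explain 20%, it rises by 48.9 − 42.1 = 6.8 or 89.6 − 83.5 = 6.1 points. At R2 of 5% the gain is about half a point. The SD of 8 min, the two differences and the R2 range are all assumptions; the break-even of about 3.4% (3.1% at 50 per arm) depends only on the sample size and the number of covariates.

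**What to change.** In the synopsis (Secondary Analyses, Time analysis) and in section 12.4, prespecify a linear model of each time endpoint on study arm with site, age, sex and BMI, the last computed from the recorded height and weight. Report the adjusted arm difference with its 95% confidence interval. Keep the t-test as a sensitivity analysis and the planned unadjusted summaries as descriptive statistics.

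The number of sites should be settled first, because it sets the number of site terms: the synopsis plans up to 3 sites and section 9.0 up to 10.

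The cost is one sentence in each of two places, with no new data, staff or patients. The statistical price is a few degrees of freedom, about one point of power if the patient covariates turn out not to be prognostic.

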#### 4.0 Acronyms and Definitions

ADE	adverse device effect
ADL	activities of daily living
AE	adverse event
CRF	case report form
FDA	Food and Drug Administration
GCP	good clinical practice
GI	gastrointestinal
ICF	informed consent form
IFU	Instruction for use
ICH	International Conference on Harmonisation
IRB	institutional review board
ISO	International Organization for Standardization
OC	optical colonoscopy
DCBE	double contrast barium enema
CT	computed tomography

Document title:  Optimizing the Preparation Regime Prior to Colonoscopy Procedure with Pure-Vu System	Document No.  CL00042	Version  1.0	Page 12 of 61
---	------------------------------------	---------------------------	------------------

MagC	Magnesium Citrate
SAE	serious adverse event
SADE	serious adverse device effect
USADE	unanticipated serious adverse device effect
WS	Workstation
WSC	Workstation Connector
BBPS	Boston Bowel Preparation Scale

## 5.0 Introduction

This document is a protocol for human research study. This study will be conducted in accordance with US government regulation, and applicable international standard of Good Clinical Practice, and institutional research policies and procedures.

## 5.1 Background

Colorectal cancer is the third most common cancer in men and the second most common cancer in women worldwide (2). In the United States, approximately 134,490 new cases are estimated for 2016 with approximately 49,190 deaths (8.0% of all cancer deaths) (3). Because colorectal cancer tends to develop slowly, screening and early detection can significantly reduce both the incidence and associated mortality of the disease (4).

Methods for the evaluation of subjects with suspected colonic disease include optical colonoscopy (OC) and radiologic imaging such as double contrast barium enema (DCBE) or computed tomography (CT) colonoscopy (5). While OC is considered the gold standard, patient acceptance rates are low due to perceived discomfort.

A key factor for ensuring high quality colonoscopy and successful screening is good colon preparation. Bowel preparation prior to colonoscopy is one of the major barriers to patient compliance in screening colonoscopy estimated as many as 38% of patients do not complete the bowel preparation due to palatability and/or intolerance to the large volume. Inadequate preparation is a major obstacle for achieving a high-quality colonoscopy (6). Poor bowel preparation prolongs overall screening and procedure time, decreases cecal intubation rates,

Document title:	Document No.	Version	Page 13 of 61
Optimizing the Preparation Regime Prior to Colonoscopy Procedure with Pure-Vu System	CL00042	1.0	

reduces the detection of colorectal neoplasms, increases complication rates and leads to return visits for screening which in turn leads to increased costs (7-12)

Despite the importance of good preparation, up to 25% of patients arrive for colonoscopy with inadequate bowel preparation (13) .

Pure-Vu System enables colon cleansing during standard colonoscopy using a standard colonoscope with a length of 1630mm – 1710mm and a diameter between 12.8mm – 13.7mm. The Oversleeve device, which fits over the colonoscope and is connected to an external workstation, generates fluid jets to break up the feces. The fecal matter & fluids are removed through the evacuation channels of the Oversleeve device into an external waste receptacle.

The current study is designed to evaluate the efficacy of two different reduced preparation regimen intended for use with Pure-Vu System. The study objectives are to compare cleansing levels, cecum intubation rate, the time to cecum, the total procedure time, and adverse event (AE) rates following use of the two different bowel preparation methods in subjects undergoing standard colonoscopy.

## 6.0 Investigational Device

### 6.1 General Description

The Pure-Vu System is Food and Drug Administration (FDA) approved device since September 22, 2016, intended to connect to standard colonoscopes to help facilitate intra-procedural cleaning of a poorly prepared colon by irrigating or cleaning the colon and evacuating the irrigation fluid (water), feces and other bodily fluids and matter, e.g. blood.

[figure not shown]
The Pure-Vu System comprises the following components:

- The Pure-Vu Workstation (WS) - controls the flow of gas (e.g. air) and water or saline to the Oversleeve device and the evacuation of fecal matter and fluids out of the body.
- The disposable Oversleeve is mounted on top of the colonoscope allowing the physician to clean the colon. The Oversleeve is connected to WS via the WS Connector (WSC).
- The disposable WS Connector is mounted onto the front panel of the WS and connects to the irrigation and sensing lines of the Oversleeve.

Document title:	Document No.	Version	Page 14 of 61
Optimizing the Preparation Regime Prior to Colonoscopy Procedure with Pure-Vu System	CL00042	1.0	

- The loading fixture is an ancillary device that is used to aid the nurse in loading the device on the colonoscope.
- External reservoir for collecting the evacuated fecal matter and fluids
- External foot pedals that operate the cleansing and evacuation process to be used by the investigator.

Below is a drawing showing the various components of the system and where they connect to each other.

